7.3 Vital Signs

Observed value and change from baseline of vital signs (including systolic and diastolic blood pressure, respiration rate, oxygen saturations, heart rate, and temperature) will be summarized at each analysis visit.

Observed values and changes from baseline values will be listed. In the listing, values of potential clinical importance will be flagged. These are defined as:

Table 2: Criteria for Potentially Clinically Significant Vital Signs

	Criteria		
Vital Sign Parameter	Flag	Observed Value	Change from Baseline
Systolic blood pressure	High	≥180	Increase of ≥20
(mmHg)	Low	≤90	Decrease of ≥20
Diastolic blood pressure (mmHg)	High	≥105	Increase of ≥15
	Low	≤50	Decrease of ≥15
Heart rate	High	≥120	Increase of ≥15
(beats per minute)	Low	≤50	Decrease of≥15

7.4 Electrocardiogram (ECG)

Observed values and changes from baseline for ECG parameters (including heart rate, PR interval, RR interval, QRS interval, QT interval, and QTc interval) will be summarized by analysis visit.

Clinical Protocol APL9-COV-201

Number and percentage of subjects with abnormal ECG interpretation will also be summarized at each analysis visit.

ECG data will also be presented in listing.

8. PHARMACOKINETIC ANALYSIS

8.1 Drug Concentration

The observed values and changes from baseline of APL-9 concentrations will be summarized for pharmacokinetic (PK) set at each scheduled time point using descriptive statistics (including at least mean, SD, CV, Min, Max, Geometric Mean, and %CV). The number and percentage of subjects with a BLQ value will also be tabulated. The handling of BLQ in the summary table is described in Section 8.2.

Linear and log-linear individual concentration profile plots against the actual study visit will be produced by study part and treatment group.

Linear and log-linear mean concentration plots against the actual study visit will be generated by study part and treatment group. The number of subjects contributing to each mean value at a visit will be presented above the x-axis.

A listing of concentration data will be presented by study part and treatment group. The actual time, deviation, and percent deviation from nominal time will be listed.

All summaries and analyses of the pharmacokinetic data will be based on the PK set.

8.2 Handling BLQ Values

APL-9 concentrations reported as below the limit of quantification (BLQ) will be taken as zero for linear plots, and equal to the lower limit of quantification (LLOQ) for semi-logarithmic plots. For the computation of descriptive statistics, BLQ will be taken as zero, except for the calculation of the geometric mean where the LLOQ will be used.

For the estimation of PK parameters, concentrations that are recorded as BLQ prior to the first quantifiable value will be set to 0. Concentrations that are recorded at the end of the sampling period (i.e. no further quantifiable concentrations) will be set to missing and will not be used for the estimation of parameter values. If a BLQ value falls between two quantifiable concentrations the value will be set equal to the LLOQ, unless its exclusion can be justified (e.g. implausibility given the profile observed and known PK properties).

9. PHARMACODYNAMIC ANALYSIS

9.1 Pharmacodynamic Data

The pharmacodynamic (PD) endpoints will be evaluated using the PD Population.

Observed values, changes from baseline and percentage changes from baseline in PD endpoints will be summarized by study part and treatment group at each protocol specified time point using descriptive statistics. PD markers include the following:

- complement activation (C3, C3a, C4, C4a, Bb, C5a, TCC, and alternative complement pathway hemolytic activity [AH50]),
- coagulopathy (reticulocyte count, schistocytes, lactate dehydrogenase, D-dimer, ferritin, haptoglobin, fibrinogen),
- inflammatory cytokines (C-reactive protein, tumor necrosis factor α , IL-1 β , and IL-6).

Spaghetti plots for individual observed values and individual changes from baseline will be presented graphically. Actual sampling times will be used for the graphical presentation of individual data

Observed values, changes from baseline, and percentage changes from baseline will also be presented graphically by study part and treatment group. Nominal sampling times will be used for the display in plots.

PD parameters will be listed together with changes from baseline and percentage changes from baseline by study part and treatment group.

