## 6.1.2. Secondary Objectives

The secondary objectives of this study are to evaluate the effect of APL-9 on:

- Hospital length of stay
- Overall survival
- Change in Sequential Organ Failure Assessment (SOFA) score
- Time on mechanical ventilation
- Time on oxygen therapy
- APL-9 PK
- APL-9 pharmacodynamics (PD; the effect of APL-9 on complement, coagulation, and inflammation biomarkers)

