## 6.2.2. Secondary Objective Endpoints

- Hospital length of stay (measured in days)
- Any-cause mortality (measured from beginning of treatment until the safety follow-up assessment 30 days after last study treatment [up to and including Study Day 51 with a +7-day window])
- SOFA score
- Total duration of mechanical intervention (measured in days)
- Total duration of oxygen therapy (by continuously worn mask or nasal cannula, measured in days)
- APL-9 PK parameters
- Observed values and changes from baseline in markers of complement activation (C3, C3a, C4, C4a, Bb, C5a, TCC, and alternative complement pathway hemolytic activity [AH50]), coagulopathy (reticulocyte count, schistocytes, lactate dehydrogenase, D-dimer, ferritin, haptoglobin, and fibrinogen), and inflammatory cytokines (C-reactive protein [CRP], tumor necrosis factor α [TNFα], IL-1β, and IL-6).

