### 12.3.2. Analysis of Secondary Efficacy Endpoints

Continuous variables will be summarized using descriptive statistics (eg, median and mean); for categorical variables, the frequency and percentage in each category will be displayed. Time-to-event data (such as time to hospital discharge and time to mechanical ventilation discontinuation) will be summarized using Kaplan-Meier estimates accounting for censored observations (and analyzed using the Cox proportional hazard model if appropriate).

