6. EFFICACY ANALYSIS

All efficacy analyses will be summarized for each study part. Efficacy data will also be analyzed by treatment group in Part 2. Hypothesis testing will be performed for part 2 between two treatment groups.

Unless otherwise specified, baseline for all efficacy analyses is defined as the last non-missing measurement recorded prior to taking the first dose of study drug.

All CIs will be presented as 2-sided 90% and/or 95% CIs. All statistical tests will be 2-sided hypothesis tests performed at the 10% level of significance.

The primary efficacy analyses will be performed for full analysis set (FAS). The supportive efficacy analyses will be performed for Intent-to-Treat (ITT) set.

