12. DATA HANDLING CONVENTIONS

12.1 General Data Reporting Conventions

Categorical variables will be tabulated as number of subjects and percentage of total number of subjects in the given analysis set as noted for each category. Percentages will be reported to one decimal place.

Descriptive statistics will be used to summarize continuous variables including number of subjects, mean, standard deviation (SD), median, first quantile (Q1), third quantile (Q3), minimum, and maximum. Mean, median, Q1 and Q3 will be reported to 1 more decimal place than the raw data, while the SD will be reported to 2 more decimal places than the raw data. Minimum and maximum will be reported the same as the original data.

In general, all analyses will be performed by study part and treatment groups unless otherwise specified. Subject specific listings will be provided by study part, treatment, subject ID, visit and date, if applicable.

All summaries and statistical analysis will be performed by SAS v9.4 or later.

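### The pharmacodynamic secondary endpoints get only raw-scale descriptive statistics: mean percentage change is biased upward for skewed markers, and no APL-9 versus vehicle estimate is planned.

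*SAP*

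**What the plan says.** Protocol 6.1.2 lists as a secondary objective "APL-9 pharmacodynamics (PD; the effect of APL-9 on complement, coagulation, and inflammation biomarkers". The matching endpoint in Protocol 6.2.2 begins "Observed values and changes from baseline in markers of complement activation" and goes on to coagulopathy and inflammatory markers. Percentage change is not in the endpoint definition; SAP 9.1 adds it: "Observed values, changes from baseline and percentage changes from baseline in PD endpoints will be summarized by study part and treatment group". SAP 9.1 also plans individual and group plots and listings.

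SAP 12.1 defines descriptive statistics for continuous variables as the number of subjects plus "mean, standard deviation (SD), median, first quantile (Q1), third quantile (Q3), minimum, and maximum". Protocol 12.3.2 is in line with this: "Continuous variables will be summarized using descriptive statistics (eg, median and mean").

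The PK section differs. SAP 8.1 specifies statistics "including at least mean, SD, CV, Min, Max, Geometric Mean, and %CV", with log-linear plots, and SAP 8.2 gives a rule for values below quantification when the geometric mean is computed. SAP 9 has no counterpart.

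Between-arm testing appears only in the efficacy section, SAP 6: "Hypothesis testing will be performed for part 2 between two treatment groups", and "All statistical tests will be 2-sided hypothesis tests performed at the 10% level of significance". Neither SAP 6 nor SAP 9 defines a PD contrast.

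**The concern.** Percentage change is asymmetric: a tenfold rise counts as +900% and a tenfold fall as −90%. If a marker is right-skewed and varies within subjects, a few large rises dominate the arithmetic mean, which is then positive even when the distribution has not moved. A reader shown that mean, or a group plot of it, could misjudge the size of an effect and in extreme cases its direction.

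Separately, the objective is an effect of APL-9, and Part 2 is randomized against vehicle with about 30 subjects per arm. The plan sets the two arms side by side but gives no estimate of the difference or ratio, no interval, and no adjustment that uses baseline as a covariate. At this sample size that leaves precision unused.

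**Working it through.** **The plan's own figures.** The only design calculation is the chance of seeing at least one SAE with 30 subjects (Protocol 12.1, SAP 3.2). It reproduces as 1−(1−p)^30: 95.8%, 26.0%, 70.6% and 88.7% at p = 10%, 1%, 4% and 7%. There is no such figure for PD.

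**Inputs.** From the documents: 30 per arm, 1:1 allocation, two-sided 10% (the efficacy-section level, borrowed for illustration). Assumed: a lognormal marker, log-SD s at both visits, correlation r, and the true effects below.

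**Step 1: expected mean percentage change with no true change.** The log change D has mean 0 and variance s² + s² − 2rs² = 2s²(1−r). So E[exp(D)] = exp(s²(1−r)), and the expected mean percentage change is exp(s²(1−r)) − 1.

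| s | r | s²(1−r) | Expected mean % change |
|---|---|---|---|
| 0.2 | 0.9 | 0.004 | +0.4% |
| 0.2 | 0.3 | 0.028 | +2.8% |
| 0.5 | 0.5 | 0.125 | +13% |
| 0.7 | 0.6 | 0.196 | +22% |
| 0.7 | 0.4 | 0.294 | +34% |
| 1.0 | 0.6 | 0.400 | +49% |
| 1.0 | 0.4 | 0.600 | +82% |

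The sample mean of 30 such values is itself skewed, so the typical trial shows slightly less than the expectation. Over s = 0.7 to 1.0 and r = 0.4 to 0.6, the median simulated trial has an arm mean of about +21% to +74%.

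**Step 2: the other planned summaries in the same situation.** The population median percentage change is 0. In those same settings the median of 30 subjects averages about +1% to +4%. The mean raw change averages about 0. The inflation is the same in both arms, so the between-arm difference in mean percentage change averages about 0 but is noisy: its SD is 56 percentage points at s = 1, r = 0.5.

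**Step 3: a true 50% fall.** Expected mean percentage change is 0.5·exp(s²(1−r)) − 1. At r = 0.5 this is −43% for s = 0.5, −18% for s = 1 and +54% for s = 1.5.

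**Step 4: the value of baseline adjustment.** On the log scale, a change score has variance 2s²(1−r) and ANCOVA has s²(1−r²). The ratio is (1+r)/2: 0.65, 0.75 and 0.85 at r = 0.3, 0.5 and 0.7.

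**Step 5: illustrative power** (simulation, 30 per arm, two-sided 10%):

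| s | r | True APL-9/vehicle ratio | t-test, % change | t-test, log change | Log ANCOVA |
|---|---|---|---|---|---|
| 1.0 | 0.4 | 0.60 | 42% | 56% | 68% |
| 1.0 | 0.5 | 0.60 | 50% | 63% | 72% |
| 1.0 | 0.7 | 0.60 | 72% | 81% | 86% |
| 0.5 | 0.5 | 0.75 | 67% | 71% | 81% |

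At s = 0.7, r = 0.6 and ratio 0.60, the first and last columns are 89% and 97%. With no effect, the percentage-change test and log ANCOVA both reject in about 9% to 10% of trials. In the first row, 14 of the 26 points between first and last column come from the log scale and 12 from baseline adjustment.

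**The case against.** The best defence is that descriptive PD reporting is a legitimate choice in a phase 1/2 trial whose primary objective is safety, and that SAP 9.1 gives more than one statistic. That defence stands against four stronger readings that a reader might infer.

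- **That PD rests on mean percentage change alone.** It does not. Observed values, raw changes, medians and quartiles are all planned, and Step 2 shows that these stay close to no change.
- **That the vehicle arm and baseline go unused.** Vehicle is summarised beside APL-9 and would expose the inflation, and baseline enters every change score. What is absent is a formal contrast and covariate adjustment.
- **That the plan has 42% power for PD.** No PD test is planned. Step 5 illustrates precision lost under assumed values and is not a property of the plan.
- **That differences between local laboratories favour logs.** A constant laboratory factor cancels in a percentage change exactly as it does in a log ratio. Protocol Table 2 also sends the cytokines, C3a and C5a to central or specialty laboratories.

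The size also depends on skewness that the documents do not report; at s = 0.2 the bias is negligible. Finally, the remedy has a price in chance findings. SAP 9.1 lists 19 markers, 18 without schistocytes, so with 90% intervals about 18 × 0.10 = 1.8 would exclude a ratio of 1 if APL-9 did nothing.

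None of this supplies the missing geometric summary or the missing estimate of the effect named in the objective.

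**Conclusion.** The point holds as a weakness of summary and precision, not as an error in a stated figure. Mean percentage change, which SAP 9.1 adds beyond the endpoint definition, is biased upward for skewed markers. The expected bias is +22% to +82% at s of 0.7 to 1.0 and r of 0.4 to 0.6, and 0.4% to 2.8% at s = 0.2 with r of 0.9 to 0.3. These rest on an assumed lognormal shape with equal spread at both visits; the documents do not say which markers behave this way. The planned medians and the vehicle column limit the harm.

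The firmer part needs no assumption: PK is given a geometric mean and PD is not, and the plan yields no APL-9 versus vehicle PD estimate or interval although the effect of APL-9 is the objective. A change is worthwhile mainly because it is cheap.

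**What to change.** In SAP 9.1:

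1. For each continuous PD marker, add the geometric mean and the geometric mean ratio to baseline by arm and time point. With no true change this ratio is 1.00 for any s and r.
2. Wherever percentage change is kept, including in group plots, lead with the median and interquartile range.
3. For Part 2, report the APL-9/vehicle ratio of geometric means with a 90% CI from a log-scale model with treatment, log baseline and the two randomization factors (mechanical ventilation, age). Name one time point, for example Day 7, or use repeated measures over Days 3, 5 and 7. Label these analyses exploratory, without multiplicity adjustment.
4. Report schistocytes as present or absent. The Protocol synopsis and 11.6 define the parameter as presence, and a percentage change has no value when the baseline is zero.
5. Confirm that the detection-limit rule in SAP 12.6.7 applies to all PD markers, so that logarithms are defined, and state how subjects without a Day 7 sample, including deaths, are handled. The model alone does not settle that last question.

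The cost is SAP wording and one model per marker, using baseline values and strata already collected. No new data are needed. The downside is several unadjusted intervals, some of which will exclude 1 by chance.

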10. INTERIM ANALYSIS

There is no planned interim analysis.

11. INDEPENDENT DATA MONITORING COMMITTEE

The independent data monitoring committee (DMC) for this study will be appointed by the sponsor in accordance with its standard procedures. The remit, roles, and responsibilities of the DMC will be specified in a separate DMC charter. The analysis will be performed based on a separate statistical analysis plan.

12. DATA HANDLING CONVENTIONS

12.1 General Data Reporting Conventions

Categorical variables will be tabulated as number of subjects and percentage of total number of subjects in the given analysis set as noted for each category. Percentages will be reported to one decimal place.

Descriptive statistics will be used to summarize continuous variables including number of subjects, mean, standard deviation (SD), median, first quantile (Q1), third quantile (Q3), minimum, and maximum. Mean, median, Q1 and Q3 will be reported to 1 more decimal place than the raw data, while the SD will be reported to 2 more decimal places than the raw data. Minimum and maximum will be reported the same as the original data.

In general, all analyses will be performed by study part and treatment groups unless otherwise specified. Subject specific listings will be provided by study part, treatment, subject ID, visit and date, if applicable.

All summaries and statistical analysis will be performed by SAS v9.4 or later.

12.2 Definition of Study Days

Unless otherwise stated, study days of an assessment or event are defined as number of days relative to the patient's first dose date.

- For assessment/event on/after the first dose date, study days are calculated as
 Date of assessment/event the first dose date + 1
- For assessment/event before the first dose date, study days are calculated as
 Date of assessment/event the first dose date

12.3 Definition of Baseline

Unless otherwise stated, baseline is defined as the last non-missing measurement prior to or on the first administration of study drug (Study Day 1). Baseline can be on the same date as the first dose, given the measurement is expected prior to first dose when only date information is available. If there are repeated measurements with more than one evaluable result for the visit which could not be distinguished by time, mean value will be defined as baseline.

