- b Fully eligible subjects can have screening assessments on the same day as baseline, which is defined as the day of initial study drug treatment.
- c Confirmation of SARS-CoV-2 infection may be completed more than 7 days before baseline. Presence of SARS-CoV-2 viral RNA or viral antigen may be detected in respiratory specimens (collected using nasopharyngeal or oropharyngeal swabs) with a qualitative nucleic acid amplification test (such as reverse transcriptase polymerase chain reaction), viral antigen test, or other diagnostic method that is authorized, cleared, or approved by the US Food and Drug Administration or equivalent authority for SARS-CoV-2 viral detection. Note: Serology-based antibody tests do not detect presence of virus and therefore are not considered diagnostic for active infection and cannot be used for study eligibility screening or for subsequent SARS-CoV-2 assessments.
- d Height/weight can be by subject assertion.
- e Discharged subjects who are followed up by phone will be provided with emergency study cards that include a list of symptoms associated with infections. The study card also guides subjects with instructions to contact their study physicians or seek emergency medical care if they experience any of the listed symptoms.
- f For continuous variables, the worst observed daily value will be recorded. Vital signs and ECG must be collected between the administration of the loading dose of study treatment and the initiation of the maintenance dose.
- g SOFA score variables (PaO2/FiO2 ratio or SpO2/FiO2 ratio, platelets, bilirubin, hypotension/vasopressor use, GCS score, creatinine) are detailed in Section 11.1.1 and Appendix 1.
- h A list of laboratory assessments is provided in Section 11.1.8. Blood will be collected 3 times on Day 1: (1) once prior to administration of the APL-9 bolus, (2) once as soon as possible following the bolus (within 5-10 minutes) prior to the continuous infusion, and (3) once at 2 hours after the beginning of the continuous infusion. Following that, assessments should be collected within the time frame of each calendar day. The use of silica reagents in coagulation panels should be avoided in subjects treated with APL-9.

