## 11. STUDY ASSESSMENTS AND PROCEDURES

- Day 1 is defined as the day upon which study treatment is first administered.
- The last predose assessments will be considered as baseline assessments.
- Study procedures and their timings are summarized in the SoA (Table 1). Protocol waivers or exemptions are not allowed.
- Significant safety concerns should be discussed with the sponsor immediately upon occurrence or awareness to determine whether the subject should continue or discontinue study participation.
- Adherence to the study design requirements, including those specified in the SoA (Table 1), is essential and required for study conduct.
- All screening evaluations must be completed and reviewed to confirm that potential subjects meet all eligibility criteria. The investigator will maintain a screening log to record details of all subjects screened and to confirm eligibility or record reasons for screening failure, as applicable.
- Procedures conducted as part of the subject's routine clinical management and obtained before signing of the informed consent form (ICF) may be utilized for screening or baseline purposes provided that the procedures met the protocol-specified criteria and were performed within the time frame defined in the SoA (Table 1).
- The study end-of-treatment assessments are to be conducted at the end of treatment or on the day of hospital discharge, whichever occurs later. The posttreatment follow-up assessment, conducted 30 days after the last dose of study drug (with a +7-day window), may be conducted either in the hospital or by telephone so that subjects do not have to be exposed to the hospital environment after hospital discharge.
- Discharged subjects will be provided with emergency study cards that include a list of symptoms associated with infections. The study card also guides subjects with instructions to contact their study physicians or seek emergency medical care in the event they experience any of the listed symptoms.

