#### 11.1.1. SOFA Score

Organ failure status will be assessed using the SOFA score, which assesses 6 organ systems: respiration, coagulation, liver, cardiovascular, central nervous system, and renal (Ferreira et al. 2001). A subject will be defined as being free of organ failure when the SOFA score is zero. The score will be assessed at baseline on Day 1 and as listed in the SoA based on worst daily values.

The SOFA score variables to be assessed are:

- PaO2/FiO2 ratio (mm Hg) or SpO2/FiO2 ratio—collected and entered into the database locally (see calculation instructions in Appendix 1)
- Platelets  $\times 10^3/\mu$ L—based on data provided by the local laboratory
- Bilirubin ( $\mu$ mol/L or mg/dL)—based on data provided by the local laboratory
- Hypotension/use of vasopressors—collected and entered into the database locally
- Glasgow Coma Scale score—collected and entered into the database locally (see Appendix 2)
- Creatinine (µmol/L or mg/dL)—based on data provided by the local laboratory

See Appendix 1 for additional information on calculating the SOFA score.

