## 12.4. Safety Analysis

All safety analyses will be summarized for the safety set.

Adverse events will be coded using MedDRA. All AEs, including TEAEs, will be summarized by System Organ Class, Preferred Term, and treatment group for number of subjects and proportion reporting the event. A similar summary will be produced for SAEs, AEs leading to termination, severe AEs, and AEs related to the investigational product. The intensity of AEs and the relationship to investigational product will be summarized for each System Organ Class and Preferred Term by treatment group.

Withdrawals because of AEs will be summarized for each body system and Preferred Term by treatment group.

As described in Section 11.2, TEAEs are defined as those AEs that develop or worsen after the first dose of study medication up to and including the safety follow-up assessment 30 days after the last dose of study drug (up to Study Day 51 with a +7-day window).

AE summaries will be presented across all subjects. All AEs will be listed by subject, along with information regarding onset, duration, relationship, and severity to investigational product, action taken with investigational product, treatment of event, and outcome.

All laboratory assessments will be summarized by treatment group using appropriate descriptive statistics.

Changes from baseline in clinical laboratory tests will be summarized, using descriptive statistics, by visit and nominal time after dosing, and by treatment group. Baseline will be taken as the last predose assessment. Out-of-range values will be flagged in data listings.

Changes from baseline in vital signs will be summarized, using descriptive statistics, by treatment, visit, and nominal time after dosing. Baseline will be taken as the last predose assessment.

Values of potential clinical significance will be flagged in listings and summarized by treatment.

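### The SAP baseline rule can take a reading made after the loading dose as baseline for vital signs and ECG, so the change-from-baseline results for these two assessments are unreliable as specified

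*SAP*

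**What the plan says.** **SAP.** Section 12.3 sets the general rule: "baseline is defined as the last non-missing measurement prior to or on the first administration of study drug (Study Day 1"). For records that carry a date but no time, it adds: "Baseline can be on the same date as the first dose, given the measurement is expected prior to first dose when only date information is" on record. Where a visit has several evaluable results "which could not be distinguished by time, mean value will be defined as baseline". Section 6 sets a separate, strictly predose baseline, but for efficacy analyses only. Sections 7.3 (vital signs), 7.4 (ECG) and 9.1 (pharmacodynamics, PD) give no baseline rule of their own, so 12.3 governs them.

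**Protocol.** Section 11: "The last predose assessments will be considered as baseline assessments". Section 12.4, for laboratory tests and vital signs: "Baseline will be taken as the last predose assessment". Table 1 footnote f: "Vital signs and ECG must be collected between the administration of the loading dose of study treatment and the initiation of the maintenance dose". The same footnote keeps the worst value of each day for continuous variables. Table 1 has a single screening/baseline column running from Day −7 to Day 1, with no separate post-loading column.

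**Precedence.** SAP Section 1 says the SAP overrides the protocol's analysis plan. SAP 14.1 reports no changes from the protocol's analyses.

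**The concern.** Safety is the primary objective, and SAP Section 7 counts vital signs and ECG among the safety endpoints. The loading infusion is when an acute effect on blood pressure, heart rate or ECG intervals would be expected to show, and footnote f makes sure a reading is taken then. If that reading becomes the baseline, the immediate effect cannot appear as a change, and every later change is measured from a point that already contains it.

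The protocol's baseline would prevent this. The SAP widens it without saying so, and the SAP takes precedence. Two programmers working from the same data could derive different baselines and both claim to have followed 12.3.

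**Working it through.** The plan gives no figure on this point. The check is a comparison of texts, followed by simple algebra.

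**1. Which Day 1 reading does 12.3 select for vital signs and ECG?**

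- *Times recorded, predose and post-loading readings both present.* The rule takes the latest value up to and including first administration. It does not say whether a reading minutes after the loading infusion counts as being on first administration, so the post-loading reading is not excluded.
- *Date only.* The reading is admitted because it is presumed predose. Footnote f schedules it after the loading dose, so the presumption fails.
- *Several readings that time cannot separate.* They are averaged, which can mix predose and post-loading values.

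Worst-of-day recording adds to the problem, because nothing restricts the Day 1 value to the predose period. SAP 12.4 builds its analysis windows from the schedule's visits, and the schedule has no post-loading Day 1 visit. The mandated reading therefore has no analysis slot other than baseline.

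**2. Effect on the between-arm comparison.** Let d be the acute loading-dose effect (APL-9 minus vehicle) and r the share of d still present at a later visit. Randomization makes the expected predose difference zero. The between-arm difference is then 0 at a predose baseline, d/2 at the mean of one predose and one post-loading value, and d at a post-loading baseline. The later between-arm difference is r × d, and the change is that minus the baseline difference. With an assumed d = 10 units:

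| Share persisting, r | Predose: r × d | Mean of the two: r × d − d/2 | Post-loading: r × d − d |
|---|---|---|---|
| 1 (persistent) | 10 | 5 | 0 |
| 0.5 | 5 | 0 | −5 |
| 0 (transient) | 0 | −5 | −10 |

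A persistent effect is cancelled. A transient one produces a later change of the opposite sign. The result scales with d: for d = 5 or 20 and r = 0, a post-loading baseline gives −5 or −20.

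**3. Effect on a flag.** SAP Table 2 lists, for low systolic pressure, an observed value of 90 or less and a decrease of 20 or more. Assume one subject with 120 predose, 96 post-loading and 88 on Day 2.

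- Predose baseline: 88 − 120 = −32. Both criteria are met.
- Mean baseline, (120 + 96)/2 = 108: 88 − 108 = −20. Both are met, the change exactly at its limit.
- Post-loading baseline: 88 − 96 = −8. The change criterion is not met, so there is no flag if both criteria are required.

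The fall at loading itself, 96 − 120 = −24, does not appear as a change when 96 is the baseline. The SAP does not say whether both Table 2 criteria are required. If either is enough, 88 is flagged on its observed value under all three baselines.

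**The case against.** **The proviso may be a condition.** The date-only sentence in 12.3 can be read as admitting a same-day value only if that measurement is scheduled before dosing. Readings that footnote f places after loading would then not qualify. This is a fair reading, and it means the SAP is ambiguous; it does not plainly choose a post-loading baseline. But it covers date-only records alone and leaves timed readings on the day of first administration unresolved.

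**A reader might infer that the whole safety comparison is compromised.** The documents do not support that. The primary endpoint is TEAE and SAE incidence, which uses no vital-sign baseline. Protocol 11.1.5 requires confirmed, clinically significant vital-sign changes to be recorded as adverse events. Infusion-related reactions, observed values and abnormal-ECG counts are also reported without subtraction. Nor can one say that only the APL-9 arm is distorted: vehicle subjects also receive a 50-mL infusion, and any drug effect is an assumption. Protocol 7.3 says this dose and higher ones were well tolerated in healthy volunteers.

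**A reader might extend the point to SOFA.** SOFA is an efficacy analysis, and SAP Section 6 already requires a predose baseline for it. What remains is protocol 11.1.1: "The score will be assessed at baseline on Day 1 and as listed in the SoA based on worst daily values", which carries no predose limit on Day 1.

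**A reader might extend it to PD markers.** With 80% suppression, averaging one predose and two postdose draws gives (100 + 20 + 20)/3 = 46.7, and the apparent fall is (20 − 46.7)/46.7 = −57%. That happens only if draw times are lost. The three Day 1 draws are separately timed in the protocol, and SAP 9.1 summarizes by scheduled time point and plots individual data at actual sampling times.

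**A reader might infer a large excess of false high flags on Day 2.** Assume a transient 15 mm Hg fall and a within-subject SD of 8. The SD of a difference is 8 × √2 = 11.3, and with a post-loading baseline about 33% would show a rise of 20 or more, against 4% by chance. But Table 2 also lists an observed systolic value of 180 or more. With an assumed mean of 125 and total SD √(15² + 8²) = 17, about 0.06% reach 180. If both criteria apply, almost nobody is flagged.

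**Conclusion.** The point holds for vital signs and ECG. SAP 12.3 can select a post-loading baseline, contrary to protocol Sections 11 and 12.4, and SAP 14.1 does not declare the departure. The exposed outputs are the change-from-baseline summaries for both assessments and the change-based flags for blood pressure and heart rate. The bias in the between-arm change is −d for a post-loading baseline and −d/2 for a mean of two readings, whatever share of the effect persists.

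No sample-size or error-rate figure changes. The values of d, r and blood pressure above are illustrative assumptions, because the documents give no estimate of an acute effect. How many subjects would be affected is unknown. Protocol 9.4 has dose times recorded in the eCRF, but the documents do not show whether it captures clock times for vital signs and ECG. The defect is confined to descriptive safety results, but it concerns a stated rule and should be corrected before those tables are produced.

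**What to change.** **In SAP 12.3:**

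- Define the safety and PD baseline as the last non-missing value before the start of the loading infusion, using recorded times.
- Do not presume that a date-only Day 1 vital sign or ECG value is predose. Use the latest earlier screening value if there is one; otherwise treat baseline as missing.
- Never average predose with postdose values.

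**In SAP 7.3, 7.4 and 12.4:** summarize the post-loading Day 1 vital signs and ECG as their own post-baseline time point, with change from the predose value.

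**For SOFA:** state only that the Day 1 baseline uses predose values, in line with SAP Section 6.

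**Across documents:** reconcile protocol Table 1 footnote f with protocol Sections 11 and 12.4.

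**Cost:** SAP wording and a clock-time check on Day 1 records. Some subjects may have a baseline from earlier in the screening window, which opens on Day −7, or none. The number depends on whether the eCRF captures assessment times, so that should be checked first.
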